Using a randomized controlled trial (RCT) design, we will enroll informal HF caregivers with poor self-care (Health Self-Care Neglect scale score ≥2), randomizing them 1:1 to an intervention or control group. Both groups will receive standard care augmented with Health Information (HI) delivered through the Internet, but the ViCCY caregiver group will also receive 10 front-loaded coaching support sessions tailored to individual issues. The control group will have access to the same HI resources over the same interval, using the same Internet program, but without coaching support. At baseline and 3, 6, 9, and 12 months, we will collect self-reported data on self-care, stress, coping, and health status. At 6 months, we will compare the efficacy of ViCCY (HI plus coaching) to HI alone to assess intervention efficacy using intent-to-treat analysis. Our pilot data suggest that addition of support provided by the health coach will make ViCCY more efficacious than HI alone. A sample of 250 caregivers (125/arm) will provide >90% power to detect significant differences between the groups on the primary outcome of self-care (Aim 1). We will collect quality adjusted life years (QALYs) and health care resource use in caregivers over 12 months to assess cost-effectiveness of ViCCY (Aim 2). To explore the effect of caregiver outcomes on HF patients' outcomes over a 12-month period (Aim 3) and knowing that not all HF patients will participate, we will consent a subgroup of the HF patients cared for by these caregivers (at least 40 dyads). We have the following Specific Aims:

- Aim 1: To compare the efficacy of ViCCY vs. HI alone in improving self-care. We hypothesize that, at 6 months after enrollment, caregivers randomized to ViCCY vs. HI alone will have **H1a**: Improved self-care measured with the Health Self-Care Neglect scale (*primary outcome*); **H1b**: Less self-reported stress measured with the Perceived Stress Scale (*secondary outcome*); **H1c**: Better coping measured with the Ways of Coping Questionnaire, short form(*secondary outcome*); and **H1d**: Better perceived mental and physical health status measured with the SF-36(*secondary outcome*).

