ViCCY over 6 months. Assessments of self-care, perceived stress, coping, and health status will be conducted at baseline (after enrollment but prior to randomization) and by phone at 3, 6, 9 and 12 months. Using contrasts within a mixed-effect modeling framework, we will assess intervention efficacy at 6 months using intention-to-treat analysis. We chose to provide 10 health coaching sessions based on our pilot data and literature demonstrating that a shorter duration of health coaching is not routinely effective. Ye chose to assess the primary aim at 6 months based on prior psychosocial intervention studies, \$3,125,155 but we will assess outcomes at 3-month intervals based on this rationale: baseline (enrollment), to generate consistent profiles of all enrollees at a consistent point in time and prior to implementation of the new intervention; at 3-months, very early effects, at 6-months, short-term effects; and at 12-months, the longer-term effects of ViCCY vs. HI. These 3-month intervals also will allow us to compare our results with others. Ye chose a 12-

month follow-up interval for the cost-effectiveness analysis to allow for a full year of event accrual. We will pull resource use data from the electronic medical record (EMR) in 30 day increments and validated these data during routine follow-up calls with caregivers. We expect the proposed study to require 5 years for completion.

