To assess changes in each of the primary and secondary outcomes over time, separate mixed effects regression models will be generated with SAS Proc Mixed. 265 We are not powered for secondary outcomes (e.g., stress, coping, health status), but we will examine effect sizes and confidence intervals (CIs) to determine if lack of power is driving nonsignificant results. Mixed models can account for correlation between repeated measures and handle non-excessive MAR or MCAR data better than traditional models and allow for use of time-independent and time-dependent covariates. Both random slopes and random intercepts will be modeled to represent deviations from the average, or fixed-effect, slope over time and intercept, respectively. REML will be used for parameter estimation and the most appropriate covariance structure will be examined. Scores will be analyzed as repeated observations, with mean-centered baseline outcome scores serving as a covariate. Other predictor variables will include group, assessment time, and the interaction of group time (primary effect of interest). Baseline measures and group will be analyzed as time-independent covariates. The evaluation of differences in outcome profiles over time according to group will rely on the group x time interaction terms, while differences by the balancing variables will rely on the mixed-effects modeling of higher order interaction terms. 267-270 Statistical significance for individual intervention contrasts will be evaluated for each outcome, applying the Benjamini & Hochberg method to control for the type I error rate at 5%. The Akaike information criterion (AIC) will be used to evaluate overall model fit and to select the best-fitting longitudinal change pattern. We expect the groups to be balanced on baseline characteristics due to randomization; however, imbalances that occur by chance will be adjusted for in all analyses. Time-dependent covariates of perceived stress and potential moderating effects of natural support or an intervening hospitalization will be examined in exploratory models. Using methods described above, time-specific contrasts will be estimated to evaluate differences in outcome within groups at 9 and 12 months.

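### C.14 labels a baseline-adjusted group-by-time interaction as the primary effect, which matches neither the 6-month difference in H1a and C.3 nor the interaction powered in C.13

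*Combined protocol and SAP*

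**What the plan says.** Four parts of the combined protocol and SAP bear on the primary test.

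- **Specific Aims, Aim 1 (H1a).** The primary hypothesis is tied to one time point and is between groups: "We hypothesize that, at 6 months after enrollment, caregivers randomized to ViCCY vs. HI alone will have" better self-care on the Health Self-Care Neglect (HSCN) scale.
- **C.3 Study Overview.** "Using contrasts within a mixed-effect modeling framework, we will assess intervention efficacy at 6 months using intention-to-treat analysis".
- **C.13 Power.** Mean HSCN is assumed to be 3.2, 1.25, 1.1 (ViCCY) and 3.2, 3.0, 2.7 (HI) at baseline, 3 and 6 months. Three assessment points with 100 per arm are said to give 90% power for group x time. Baseline is one of the three, and C.13 describes its mixed-model design as consistent with the primary analysis.
- **C.14 Data Analysis Plan.** On baseline: "Scores will be analyzed as repeated observations, with mean-centered baseline outcome scores serving as a covariate". On the test: "Other predictor variables will include group, assessment time, and the interaction of group time (primary effect of interest"). On time: "Both random slopes and random intercepts will be modeled to represent deviations from the average, or fixed-effect, slope over time and intercept". AIC is used "to evaluate overall model fit and to select the best-fitting longitudinal change pattern". Contrasts appear in general terms ("Statistical significance for individual intervention contrasts will be evaluated for each outcome"). The only time-specific contrasts it spells out are these: "time-specific contrasts will be estimated to evaluate differences in outcome within groups at 9 and 12 months".

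**The concern.** What a group x time interaction measures depends on whether baseline is among the responses. If it is, the interaction compares the arms' departures from a common starting point and so captures the treatment effect. If baseline is only a covariate, the treatment effect moves into the group term, and the interaction asks only whether the gap between arms changes from one follow-up visit to the next. A benefit that appears by month 3 and persists, which is close to what C.13 assumes, then produces almost no interaction.

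C.14 is the section an analyst would program from. It specifies the covariate form and gives the primary label to the interaction. H1a and C.3 point to the 6-month difference. Two results could then each be called primary and could disagree. The slope wording and the AIC step also leave the shape of time, and so the meaning of the interaction, to be settled after the data are seen.

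**Working it through.** **Inputs, all from C.13.** HI minus ViCCY gaps are 0, 1.75 and 1.60 at months 0, 3 and 6. SD is 2.8 at every visit (variance 7.84), first-order autocorrelation is 0.3, and there are 100 evaluable per arm at the 5% level. C.13 does not state sidedness; I take two-sided.

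**C.13's own figures**
- Overall means: (3.2 + 1.25 + 1.1)/3 = 1.85 and (3.2 + 3.0 + 2.7)/3 = 2.97, difference 1.12. This agrees with C.13 and with 0.4 x 2.8 = 1.12.
- Enrolment: 200/0.8 = 250. This agrees.
- Overall group effect: about 98% (stated 99%). Time effect: 99.9% (stated 99%).
- Group x time, stated 90%: no model I tried gives exactly 90%. C.13 used 100 iterations, and the exact 95% interval for 90 out of 100 is 82.4% to 95.1%.

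**General formula.** For a contrast with effect d and per-person variance v, SE = sqrt(2v/100). Power comes from the noncentral F distribution with noncentrality (d/SE)² and 198 denominator df.

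**(a) C.14 taken literally: baseline a covariate only, responses at months 3 and 6**
- Effect: 1.75 − 1.60 = 0.15.
- Variance of the month 3 to 6 change: 2 x 7.84 x (1 − 0.3) = 10.976.
- Covariance of that change with baseline: 7.84 x (0.09 − 0.3) = −1.646. Conditional variance: 10.976 − 1.646²/7.84 = 10.630.
- SE = sqrt(2 x 10.630/100) = 0.461. Noncentrality = (0.15/0.461)² = 0.106.
- **Power 6.2%.** With two response visits, linear and categorical time are the same model, so time coding does not matter here.

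**(b) 6-month difference, baseline as covariate**
- v = 7.84 x (1 − 0.09²) = 7.776. SE = 0.394. Noncentrality = (1.60/0.394)² = 16.46.
- **Power 98.1%.**

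**(c) Baseline as a response, months 0/3/6, categorical time (2 df)**
- Changes from baseline: 1.75 and 1.60. Their variances are 10.976 and 14.269, and their covariance is 7.84 x 0.91 = 7.134, each multiplied by 2/100.
- Noncentrality = 15.06. **Power 94.2%.**

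**(d) Baseline as a response, months 0/3/6, linear time**
- With three equally spaced visits and this correlation, the weighted slope puts weights −1/2, 0, +1/2 on the visits. The interaction is 1.60/2 = 0.80 per visit, exactly half the baseline-to-6-month change contrast, so the two tests are identical.
- v = 2 x 7.84 x (1 − 0.09) = 14.269. SE of the change contrast = 0.534. Noncentrality = (1.60/0.534)² = 8.97.
- **Power 84.6%.**

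**How often (a) and (b) disagree.** In 5,000 simulated trials on C.13's inputs, the baseline-adjusted 6-month difference was significant and the month 3 versus 6 interaction was not in 92.7%.

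**Sensitivity.** With an assumed correlation of 0.5 instead of 0.3, (a) is 6.8%, (b) 98.6%, (c) 98.4% and (d) 90.7%. The pattern is unchanged.

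**The case against.** The strongest reply is that the authors plainly did not intend reading (a). A test with 6% power could not have produced 90 successes in 100 simulations, so the model behind C.13 must keep baseline among the responses. On that model with linear time, the interaction is the baseline-to-6-month change contrast; with categorical time, its 6-month term is that contrast. C.3's reference to contrasts then fits, and the 6-month timing is repeated elsewhere in the protocol. This stands as an account of intent. It does not change what C.14 instructs, which is baseline as a covariate and the interaction as primary. It shows that C.13 and C.14 describe different models.

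Four stronger readings are tempting, and the documents do not support them.

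- *Power is anywhere from 6% to 94%, all equally open.* No. C.14 does state baseline's role as a covariate, and C.13 rules out the 6% model as the source of its own figure. What C.14 leaves unsaid is whether baseline also stays among the responses.
- *The stated 90%, or the sample of 250, is wrong.* No. Both 85% and 94% lie inside the simulation error of 90 out of 100.
- *The plan has no 6-month between-group test.* No. C.3 supplies one. The available text has headed subsections C.14.2 and C.14.3 but no C.14.1, so absence cannot be claimed.
- *The interaction is also weak or strong once months 9 and 12 enter.* C.13 gives no means after month 6, so this cannot be computed from the documents.

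**Conclusion.** The point holds as a mismatch between sections. C.14's model and primary label do not agree with the 6-month difference in H1a and C.3, or with the three-visit interaction in C.13. Followed as written, C.14 makes the labelled primary test nearly blind to the benefit the plan assumes: about 6% power against about 98% for the baseline-adjusted 6-month difference, with the two disagreeing in that direction in about 93% of trials. If baseline is a response, the labelled test has about 94% or 85% power and the practical conflict is much smaller.

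These figures rest on C.13's means, SD and correlation, 100 evaluable per arm, a two-sided 5% level, and data through month 6. The 6% and 93% apply only to the literal covariate-only reading.

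**What to change.** In C.14:
- Name one primary test: the ViCCY minus HI difference in HSCN at 6 months, two-sided 5%, from the mixed model with visit as categorical.
- Remove the primary label from the group x time interaction.
- Use baseline once, chosen in advance: either as a covariate with post-baseline visits as responses, or as a response with a baseline-to-6-month contrast. State which visits are responses.
- Do not let AIC choose the shape of time for the primary test.

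In C.13, state power for the chosen contrast at the assumed 1.60-point difference with 100 per arm: about 98% with baseline as a covariate, or about 85% for the change contrast.

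The cost is a few sentences of SAP wording and one restated power figure. No caregivers, visits or data are added.

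### C.14 names only REML and lets AIC choose the change pattern; if AIC comes from REML fits with different numeric time terms, the comparison is invalid and depends on the unit of time

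*Combined protocol and SAP*

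**What the plan says.** C.14 (Data Analysis Plan, Aim 1 models) states that "separate mixed effects regression models will be generated with SAS Proc Mixed", one for each primary and secondary outcome. On estimation it says: "REML will be used for parameter estimation and the most appropriate covariance structure will be examined". A few sentences later, AIC "will be used to evaluate overall model fit and to select the best-fitting longitudinal change pattern".

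Time appears as a numeric trend: "Both random slopes and random intercepts will be modeled to represent deviations from the average, or fixed-effect, slope over time and intercept, respectively". Repeated scores are analysed "with mean-centered baseline outcome scores serving as a covariate", so the modelled outcomes are the follow-up assessments, collected "by phone at 3, 6, 9 and 12 months" (C.3). The group-by-time interaction is named as the effect of primary interest. The Specific Aims and C.3 place the efficacy comparison at 6 months, and C.3 says that it will use contrasts from the mixed model.

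C.14 does not list the candidate patterns, give the unit of time, say which likelihood AIC is computed from, or say how parameters are counted in its penalty.

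**The concern.** Covariance structure has its own sentence in C.14, so the change pattern most naturally means the shape of the mean over time: a straight line, a curve, or separate visit means. Such models have different fixed effects. AIC from REML can rank covariance structures that share one mean model. It cannot rank mean models, because the REML likelihood carries a term that changes with the columns and scaling of the fixed-effect design, apart from fit.

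At stake is prespecification. The 6-month contrast is read from the selected model, so an unstated coding choice could decide which model is reported, for the primary and every secondary outcome.

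**Working it through.** **Inputs.** From C.13: 100 completers per arm, SD 2.8 at every time, first-order autocorrelation 0.3, and means at 0, 3 and 6 months of 3.2, 1.25, 1.1 (ViCCY) and 3.2, 3.0, 2.7 (HI). From C.3 and C.14: follow-up at 3, 6, 9 and 12 months, baseline as covariate, random intercept and slope. Assumed, because the documents do not give them: 9- and 12-month means, complete data, normal scores, and the candidate patterns.

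**The plan's own figures.** 200/(1 − 0.20) = 250. The overall means are (3.2 + 1.25 + 1.1)/3 = 1.85 and (3.2 + 3.0 + 2.7)/3 = 2.97, a difference of 1.12 = 0.4 × 2.8. Recomputed power is 98.1% (group), 99.9% (time) and 94.3% (interaction), against 99%, 99% and 90% stated. The last gap of 4.3 points is compatible with 100 iterations, whose standard error is √(0.9 × 0.1/100) = 3 points. The inputs are therefore read as intended, and this point disputes none of these figures.

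**The algebra.** −2 × the REML log-likelihood contains log|X′V⁻¹X|. Multiplying one column of X by k adds 2 ln k. The random slope variance rescales with time, so V and the fitted values do not change. From months to years:
- Each t column is divided by 12, a change of −2 ln 12.
- Each t² column is divided by 144, a change of −2 ln 144 = −4 ln 12.
- Linear model (t and group × t): −4 ln 12 = −9.94.
- Quadratic model (also t² and group × t²): −4 ln 12 − 8 ln 12 = −12 ln 12 = −29.82.
- Visit as category: 0.

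The linear-versus-quadratic difference therefore moves by 8 ln 12 = 19.88. This needs no assumed effect.

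**One simulated trial.** REML AIC in years is 3844.74 (linear) and 3831.45 (quadratic), so quadratic wins by 13.29. In months it is 3854.68 and 3861.27, so linear wins by 6.59. The swing is 13.29 + 6.59 = 19.88. Maximum-likelihood AIC is 3847.26 and 3844.23 in both units.

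**How often the choice changes.** 300 trials per shape, with the REML AIC penalised for the 4 covariance parameters only. The entries are the share preferring quadratic to linear:

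| Assumed shape after 6 months | REML, years | REML, months | Choice flips | ML, either unit |
|---|---|---|---|---|
| Plateau | 100% | 0.7% | 99% | 23% |
| Straight line from 3 to 12 months | 100% | 0.3% | 99.7% | 16% |
| Effect wanes | 100% | 5% | 95% | 56% |

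Counting fixed effects in the penalty adds 4 points to the quadratic-minus-linear difference in both units. The plateau average goes from −8.95 and +10.93 to about −5 and +15, so the sign still changes.

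Months coding is no safeguard. When the true trend is straight, REML AIC in months preferred visit-as-category to the straight line in 100% of trials, against 6% by maximum likelihood.

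**Effect on the 6-month contrast (true value 1.6).** 40 trials per shape. In months, REML AIC chose category in 40 of 40 for every shape.

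| Assumed effects at 3, 6, 9, 12 months | Quadratic chosen, years | Mean estimate, months | Mean estimate, years |
|---|---|---|---|
| 1.75, 1.6, 1.6, 1.6 | 40/40 | 1.56 | 1.61 |
| 1.75, 1.6, 0.8, 0 | 40/40 | 1.56 | 1.52 |
| 1.75, 1.6, 0, 0 | 21/40 | 1.63 | 1.42 |

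The differences are 0.05, 0.04 and 0.21. Other simulation sets for the abrupt loss gave 0.14 to 0.25 (1.55 versus 1.41; 1.65 versus 1.40).

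A direct check agrees. With complete data, a quadratic through four equally spaced visits misses the 6-month value by 3/20 of the cubic contrast (−1, 3, −3, 1).
- Plateau: the contrast is −0.15, so the fitted value is 1.6 + 0.02 = 1.62.
- Waning: 0.65, giving 1.6 − 0.10 = 1.50.
- Abrupt loss: 3.05, giving 1.6 − 0.46 = 1.14 whenever the quadratic is chosen.

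For scale, the standard error of the baseline-adjusted 6-month difference is about 2.8 × √(1 − 0.09²) × √(2/100) = 0.39, where 0.09 = 0.3² is the correlation of baseline with month 6.

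**The case against.** The strongest reply is that C.14 assigns REML to parameter estimation and does not say that AIC is taken from those fits. Estimating by REML and comparing mean patterns by maximum likelihood would be compatible with the text. No candidate patterns are listed, and several places describe visit-specific contrasts. If time were categorical in every candidate, or AIC compared only covariance structures, the problem would not arise. Every assessment is stated in months, so an analyst working in years is hypothetical.

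Much of this stands. A reader might infer that the plan commits to the wrong likelihood for all outcomes. The documents do not go that far: they leave the likelihood unstated, and the reading used here is the natural one but still a reading. A reader might also infer that two analysts following the plan would report different 6-month effects. The documents give no means beyond 6 months, and under two of the three shapes above the estimate hardly moves against a standard error of 0.39. The larger shift needs the whole effect to vanish between 6 and 9 months, which no section assumes.

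What does not stand is that silence makes the rule harmless. REML is the only method named, the covariance structure is treated separately, and a fixed slope over time is described. Using months throughout fixes the unit but leaves the comparison invalid.

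**Conclusion.** The point holds conditionally. If AIC is computed from REML fits of models with different numeric time terms, as C.14 naturally reads, the selection rule is invalid. The 19.88-point dependence on the time unit is exact. That it usually flips the choice rests on simulation with the C.13 inputs, assumed 9- and 12-month effects, complete data and normal scores; a flip is not certain in every data set. The consequence for the 6-month contrast is about 0.05 under a plateau or gradual waning and about 0.2 under an abrupt loss. This is a gap in prespecification of the primary model, not evidence that the primary result will be materially biased.

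**What to change.** Preferred: in C.14, enter visit as a categorical factor with group-by-visit terms, take the 6-, 9- and 12-month contrasts from that model, and delete the AIC choice of change pattern. Keep REML, and use REML AIC only to compare covariance structures under that one mean model. The cost is four more fixed effects than a straight-line model (eight group-by-visit means instead of four coefficients), with some loss of precision if the true trend is straight.

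Otherwise: state that AIC comparisons between mean patterns use maximum-likelihood fits, list the candidates, and refit the chosen model by REML for estimates and standard errors. This is a short addition to the text and removes the dependence on the unit. It does not remove the drawbacks of choosing a pattern from the trial data: under gradual waning, the maximum-likelihood choice gave a mean 6-month estimate of 1.47 against a true 1.6.

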- **C.6.** Intervention ViCCY. In addition to augmented standard care HI, caregivers randomized to ViCCY will receive 10 front-loaded sessions of virtual health coaching by trained RNs (Section C.6.a) over 6 months with content based on the theoretical framework and our prior research (**Table 3**, next page). As shown in **Figure**

**3**, sessions are weekly initially and decrease in frequency over time. ViCCY incorporates the factors essential in caregiver interventions; it is a psychosocial approach that is personalized and tailored to be flexible; is multidimensional, providing support for coping with perceived stress while fostering self-care; and is sufficient in dose, based on our pilot work. We refined our approach based on caregiver input to focus on *relieving* stress rather than intensifying demand and burden, thereby promoting caregivers' ability to respond to stressors

with adaptive coping. We aim to build motivation to gain the knowledge and skills needed to achieve self-identified health goals. 180 We focus on identifying personal values, solving problems, and transforming goals into action using a combination of psychological and behavioral interventions. 181

We use motivational interviewing in all ViCCY sessions. 182 Observations are presented to the caregiver in a way that

2 weekly 3 biweekly 2 triweekly 3 monthly sessions sessions sessions

**Figure 3**. Intervention sequence in Virtual Caregiver Coach for You (ViCCY) Treatment Arm. A total of 10 sessions are planned with booster sessions provided if requested by the caregiver. Between sessions, caregivers will complete "homework" (i.e. strategies to use and practice), which will be reviewed by the RN to monitor how these activities worked for the caregiver. At the end of the 6-month intervention period the RN will sever the virtual relationship, referring the caregiver to the HI website for further support.

builds confidence, motivates action, and enhances self-care by breaking the cycle of negative self-perception and emotions with the knowledge, skills, and beliefs needed to engage in healthy behaviors. We discuss goal-setting and action-planning in early sessions. Consistent with motivational interviewing, information (e.g., reasons for specific patient behavior) is given only if and when the caregiver is receptive to it.

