- C.13. Power. We will enroll 250 caregivers (125 caregivers per study arm) to achieve over 90% power to detect significant overall differences in longitudinal profiles between the groups on the primary outcome of Health Self-Care Neglect Scale. 35 Assuming estimates similar to those in our pilot data, and extrapolating through 6 months, along with control group scores that also decline over time (due to interaction that comes with participation in a clinical trial) but at a slower rate than the intervention, it is assumed that ViCCY caregivers will demonstrate mean Health Self-Care Neglect scores of 3.2, 1.25, 1.1 while HI caregivers will demonstrate mean scores of 3.2, 3.0, 2.7 at baseline, 3, and 6 months, respectively. Combining the two data sets, this translates to mean scores of 1.85 and 2.97 (D=1.12) overall for intervention and control group caregivers, respectively—in line with a clinically meaningful difference equal to 0.4\*SD (SD 2.8)=1.12 units. We conservatively assumed that standard deviations (pilot estimates 2.5 and 1.3 at baseline and 3 months) are constant over time, equal to 2.8, and that the variance-covariance matrix pattern is generated using a mixed effects model design (congruent with the primary analytic plan) with a first-order auto-correlation parameter equal to 0.3. A design with three assessment points and 100 participants per group (200 total) achieves 99% power to test the overall between-group effect (intervention vs. control without regard to changes over time), 99% power to test the overall time effect, and 90% power to test the group x time interaction effect. All tests are based on simulations with 100 iterations, a 5% significance level, mean vectors and variance-covariance as described above. We anticipate 20% attrition based on our prior experience with the intervention, which was found to be helpful, supportive, and stress relieving rather than burdensome. Further, we will remunerate caregivers for their time and effort (see Human Subjects).

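### The Aim 1 plan names only within-group contrasts at 9 and 12 months, although the 12-month visit is there to compare ViCCY with HI

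*Combined protocol and SAP*

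**What the plan says.** C.3 (Study Overview) sets the primary efficacy comparison at 6 months: "Using contrasts within a mixed-effect modeling framework, we will assess intervention efficacy at 6 months using intention-to-treat analysis". It then gives reasons for the visits and assigns to the last one "at 12-months, the longer-term effects of ViCCY vs. HI". It gives no reason for the 9-month visit.

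C.14 (Data Analysis Plan) describes one mixed model per outcome, with the baseline score as a covariate and terms for group, time and their interaction. Two sentences concern differences between arms, and neither names a visit: "The evaluation of differences in outcome profiles over time according to group will rely on the group x time interaction terms", and "Statistical significance for individual intervention contrasts will be evaluated for each outcome", the latter under Benjamini-Hochberg control. The only sentence in the Aim 1 analysis that mentions 9 or 12 months closes the model description: "time-specific contrasts will be estimated to evaluate differences in outcome within groups at 9 and 12 months". It does not say which visit the within-group difference is measured from.

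Two other places bear on the point. The Figure 3 legend in C.6 says "At the end of the 6-month intervention period the RN will sever the virtual relationship". C.13 (Power) assumes "control group scores that also decline over time", which it attributes to taking part in a trial.

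**The concern.** Coaching stops at 6 months, so the 9- and 12-month visits are the trial's evidence on whether its effect lasts. That is a question about the difference between randomised arms. Change within the ViCCY arm mixes any coaching effect with whatever happens to both arms, including the improvement that C.13 expects in controls. If the change is measured from baseline, it also includes regression to the mean, because entry requires a score of 2 or more on the same scale that serves as the primary outcome.

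A statistician following the sentence as written would produce two separate within-arm results. Readers would then be tempted to infer durability from one arm being significant and the other not. Deciding on a between-arm contrast after seeing the data would be post hoc.

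**Working it through.** **Comparing the passages.** The C.3 purpose for 12 months is between arms; the C.14 contrast for 12 months is within arms. Three other parts of the plan might fill the gap:

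- The group-by-time interaction tests whether the profiles differ. It is not a statement of the 9- or 12-month difference, and an early gap that later closes could also make it significant.
- The intervention contrasts under Benjamini-Hochberg name no visit. C.3 and hypotheses H1a to H1d are set at 6 months.
- Aim 2 compares the arms over 12 months on QALYs, resource use and cost, not on self-care, stress or coping.

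**Plan figures used.** All are from C.13.

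- Mean over three visits: ViCCY (3.2 + 1.25 + 1.1)/3 = 1.85; HI (3.2 + 3.0 + 2.7)/3 = 2.97. The difference is 1.12, as stated, and 0.4 × 2.8 = 1.12.
- Sample size: 200/(1 − 0.20) = 250, as stated, leaving 100 evaluable per arm.
- SD 2.8 at all times; first-order autocorrelation 0.3.
- HI change: "HI caregivers will demonstrate mean scores of 3.2, 3.0, 2.7 at baseline, 3, and 6 months", so 3.2 − 2.7 = 0.5 by 6 months.

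The power calculation stops at 6 months, so the plan has no 9- or 12-month figure to reproduce.

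**Illustration.** Assumptions: the true change is equal in both arms, so there is no ViCCY effect; each arm is tested separately at two-sided 5%; there are 100 per arm at 12 months. The correlation r between the reference visit and month 12 is not given. With 3-month steps, 0.3⁴ = 0.008 from baseline and 0.3² = 0.09 from month 6; 0.3 and 0.5 are also shown.

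Within-arm SE = √(2 × 2.8² × (1 − r)/100), which is 0.394 (r = 0.008), 0.378 (0.09), 0.331 (0.3) and 0.280 (0.5).

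If p is the chance that one arm is significant, the chance that exactly one of the two is significant is 2p(1 − p). For a change of 0.5, p = 0.245, 0.326 and 0.431 at r = 0.008, 0.3 and 0.5. For example, 2 × 0.245 × 0.755 = 37.0%.

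Reference visit baseline, chance that exactly one arm is significant:

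| True change in both arms | r = 0.008 | r = 0.3 | r = 0.5 |
|---|---|---|---|
| 0.5 | 37% | 44% | 49% |
| 0.75 | 50% | 47% | 36% |
| 1.0 | 40% | 25% | 10% |
| 1.25 | 20% | 7% | 1% |

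Reference visit 6 months, r from 0.09 to 0.5: 9.5% with no further change (2 × 0.05 × 0.95), 18% to 25% for 0.25, and 39% to 49% for 0.5.

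Simulation with t tests (20,000 trials per cell, baseline reference) agrees within about 2 points. A baseline-adjusted between-arm comparison rejected in 4.6% to 5.1% of trials (4,000 per cell).

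**Would the direct contrast be informative?** Baseline-adjusted between-arm SE = √(2 × 2.8² × (1 − r²)/100) = 0.396 (r = 0.008) to 0.343 (r = 0.5). The 95% CI half-width is 1.96 × SE = 0.78 to 0.67 points. Power for a 1.12-point difference is 81% to 90%.

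**The case against.** The best defence is that the sentence opens by referring back to the methods already described. Those include between-arm intervention contrasts and interaction terms. If time is categorical, the interaction terms yield visit-specific group differences, so the phrase may be loose wording or a slip. All Aim 1 hypotheses are set at 6 months, so none is left untested, and Aim 2 partly covers health status at 12 months through the SF-6D. Within-arm contrasts after 6 months also have a fair descriptive use: they show whether each arm holds its level once coaching stops.

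The percentages can be challenged too. They describe an inference that the plan does not say it will make. Half of the discordant trials would have only HI significant. The tests are unadjusted although C.14 uses Benjamini-Hochberg. Because baseline is a covariate, the natural reference may be a later visit, where the figure can be as low as 9.5%. The 1.12-point difference is an average over baseline, 3 and 6 months, and 100 per arm at 12 months may be optimistic because caregivers are dropped when the patient dies (C.15).

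Much of this stands as a limit on the size of the problem. It does not remove the conflict. The sentence still ends in within groups, no other text ties a between-arm contrast to a late visit, and the plan does not say that time is categorical. If the wording is a slip, the same correction is needed.

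**Conclusion.** The concern holds. The conflict is explicit for 12 months. For 9 months the plan states no purpose, but the same sentence governs both visits. As written, no visit-specific randomised estimate is named for self-care, stress or coping after coaching ends, and the contrast that is named cannot isolate the effect of coaching. The plan does contain between-group information over time; what is missing is the stated late-visit difference.

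The illustrative size is 37% to 49% discordant within-arm results under a shared 0.5-point fall from baseline. It is 9.5% if nothing changes after a 6-month reference, and 1% to 20% for a 1.25-point fall from baseline. These rest on assumed correlations, 100 per arm, the 6-month HI change persisting to 12 months, and someone comparing the two within-arm results. The case for correction rests on the wording and does not depend on these figures. The 6-month primary comparison is unaffected. The change should be made, but it is not critical.

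**What to change.** Replace the last sentence of the Aim 1 model in C.14 with: *Time-specific contrasts from the same baseline-adjusted mixed model will estimate the ViCCY minus HI difference with 95% CIs at 9 and 12 months, as secondary analyses. Within-group changes, against a stated reference visit, will be descriptive only.* State also whether these contrasts fall within the Benjamini-Hochberg adjustment.

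The cost is one or two sentences before database lock. The model, data, visits and sample size stay the same.
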